7.9.3 Safety

All patients who receive at least one dose of DZD9008 will be included in the assessment of the safety profile (safety analysis set). At the end of the study, appropriate summaries of safety data will be produced, as defined below.

Data from all cycles of initial treatment will be combined in the presentation of safety data. AEs will be listed individually by patient and dose group. For patients who have a dose modification, all AEs (due to drug or otherwise) will be assigned to the initial dose group. The number of patients experiencing each AE will be summarized by the Medical Dictionary for Regulatory

Date: July 24,2023

Activities (MedDRA) system organ class, MedDRA preferred term and CTCAE grade. The number and percentage of patients with adverse events in different categories (eg, causally related, CTCAE grade \geq 3 etc) will be summarized by dose group in Part A and by dose cohort in Part B, and events in each category will be further summarized by MedDRA system organ class and preferred term, by dose group. SAEs will be summarized separately if a sufficient number occur.

Any AE occurring within the defined 28-day follow-up period after discontinuation of investigational product will be included in the AE summaries. Any adverse events in this period that occur after a patient has received further therapy for cancer (following discontinuation of investigational product) will be flagged in the data listings. AEs occurring after the 28 day follow-up period after discontinuation of investigational product will be listed separately, but not included in the summaries.

Hematology, clinical chemistry, vital signs and ECG data will be listed individually by patient and suitably summarized. For all laboratory variables, which are included in CTCAE 5.0, the CTCAE grade will be calculated. Summary statistics such as mean, median, standard deviation, minimum, maximum and number of observations will be used for continuous variables, frequency and percentages will be used for categorical variables.

Details of any deaths will be listed for all patients.

Any qualitative assessments will be summarized using the number and proportion of patients with results of negative, trace or positive.

Graphical presentations of safety data will be presented as is deemed appropriate. This may include, but is not restricted to, presentation of parameters against time, concentration or shift plots. Appropriate scatter plots will also be considered to investigate trends in parameters compared to baseline.

7.9.4 Pharmacokinetics

This will be summarized in the Pharmacokinetics analysis set.

Plasma concentrations of DZD9008 will be summarized by nominal sample time. Plasma concentrations and derived PK parameters will be summarized. Parameters following single and multiple dosing will be summarized separately. Plasma concentrations at each time point will be summarized according to dose by the following summary statistics:

- The geometric mean $(G_{mean}, calculated as exp[\mu], where \mu is the mean of the data on a logarithmic scale)$
- Coefficient of variation (CV, calculated as $100\sqrt{[\exp(s^2)-1]}$, where s is the standard deviation of the data on a log scale)
- $G_{mean} \pm standard deviation (calculated as exp[<math>\mu \pm s$])
- Arithmetic mean calculated using untransformed data
- Standard Deviation calculated using untransformed data

Date: July 24,2023

- Median
- Minimum
- Maximum
- Number of observations

The following summary statistics will be presented for AUC_(0-∞), AUC₍₀₋₂₄₎, AUC₍₀₋₇₂₎, AUC 168), $AUC_{(0-t)}$, AUC_{ss} , C_{max} , $C_{ss\ max}$, and $C_{ss\ min}$:

- G_{mean} , calculated as $exp[\mu]$, where μ is the mean of the data on a logarithmic scale
- CV, calculated as $100\sqrt{\exp(s^2)-1}$, where s is the standard deviation of the data on a log scale)
- Arithmetic mean calculated using untransformed data
- Standard deviation calculated using untransformed data
- Median
- Minimum
- Maximum
- Number of observations

The following summary statistics will be presented for CL/F, CL_{ss}/F, V_{ss}/F, t_{½λz}, RAC (AUC) and RAC(C_{max}), time dependency, CL_R, Ae and Fe:

- Arithmetic mean
- Standard deviation
- Minimum
- Maximum
- Number of observations

The following summary statistics will be presented for t_{max} and $t_{ss max}$:

- Median
- Minimum
- Maximum
- Number of observations

Date: July 24,2023

Regression based diagnostic parameters (λz Interval, λzN , Rsq adj, λz period/t½ λz , tlast, AUCextr) will be listed only and not summarized.

The pharmacokinetic data for DZD9008 after a single-dose and separately, at steady state will also be displayed graphically. Displays will include plasma concentration patient profiles (on the linear and log-scale) versus time and G_{mean} concentration (+/-standard deviation) versus time, stratified by dose.

Scatter plots of PK parameters versus dose, or log-dose will also be considered following both single (escalation only) and multiple dose administration of DZD9008 to assess dose proportionality in Part A.

In a preliminary assessment of dose proportionality, log-transformed $AUC_{(0-\infty)}$ and/or $AUC_{(0-t)}$ and C_{max} parameter estimates will be examined using the Power Model:

```
parameter = e^a (dose)b
i.e., log(parameter) = a + (b * log(dose))
```

where a is the intercept, depending on patients, and b is the slope, measuring the extent of dose proportionality. Dose proportionality implies that b=1 and will be assessed by estimating b along with its confidence interval.

If there is evidence of departures from dose proportionality, log-transformed dose-normalized AUC and C_{max} of DZD9008 will be analysed separately using a mixed effects model. Dose will be fitted as a fixed effect and patient as a random effect. Point estimates and associated 90% confidence intervals (CIs) for the differences between each dose level and the reference dose (the lowest dose) will be constructed using the residual variance. The estimates will then be back-transformed to provide point estimates and corresponding 90% CIs for the ratios of each dose level to the reference dose on the original scale. No adjustments for pre-planned multiple comparisons will be made. This analysis will only be performed provided there are sufficient data.

If there are more than 20% patients whose $AUC_{(0-\infty)}$ values are not calculable for either treatment due to large extrapolated area (> 20%), Rsq adjusted <0.80 or any other reason, $AUC_{(0-t)}$ will also be analyzed statistically and presented in the same way as $AUC_{(0-\infty)}$. Otherwise, $AUC_{(0-t)}$ will not be statistically analyzed.

The same analysis will be performed on AUC_{ss} and C_{ss,max} from Cycle 2 Day 1 PK data.

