6.5.1.1 Part A (Dose escalation)

Blood samples

Venous blood samples will be taken at the time points shown Table 5. Discussion with the Clinical Pharmacologist from Dizal Pharmaceuticals is required as to any impact if dose interruption occurs within 3 days of scheduled time points for PK sampling. The date and time of dosing and collection of each sample will be recorded.

Time points on Cycle 0 Day 1 are pre-dose, 0.5, 1, 2, 3, 4, 6, 8, 10, 12, 24, 48, 72, 120 and 168 hours post-dose.

Time points on Cycle 2 Day 1 are pre-dose, 0.5, 1, 2, 3, 4, 6, 8, 10, 12 and 24 hours post-dose. On Cycle 1 Day 1, Day 8, Day 15, and Cycle 3, 4, 5 Day 1, pre-dose samples are collected.

The timing for PK sampling may be adjusted with emerging data during the study, in order to ensure appropriate characterization of the plasma concentration-time profiles of DZD9008 (Table 5).

Hospitalization can be allowed for out of business time PK collection.

Blood samples (approximately 4 mL at each time point) will be collected and put into lavender top (EDTA) Vacutainer[®] evacuated collection tubes at the time points indicated. After processing, plasma samples will be split, for quantification of DZD9008 and identification and semi-quantification of all possible metabolites. The timing for PK sampling may be adjusted with emerging data during the study, in order to ensure appropriate characterization of the plasma concentration-time profiles of DZD9008.

Urine samples

Urine samples (approximately 5 mL) for the determination of concentrations of DZD9008 and characterization of its metabolites will be taken from the total urine samples provided during 0-24 h at Cycle 2 Day 1. The date and time of collection and the weight of each urine collection will be recorded. Samples will be split into aliquots, for quantification of DZD9008 and for identification and semi-quantification of all possible metabolites.

The interval for urine collection on Cycle 2 Day 1 are 0 - 4, 4 - 12, and 12 - 24 hours. The timing for PK sampling may be adjusted with emerging data during the study, in order to ensure appropriate characterization of urine excretion DZD9008.

In addition, the pharmacokinetic samples may be subjected to further analyze by Dizal Pharmaceuticals or CROs in order to investigate the presence and/or identity of additional drug metabolites. Any results from such analyses will be reported separately from the Clinical Study Report.

Food effect

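### The fallback dose-proportionality model in Protocol 7.9.4 bases its 90% intervals on a residual variance that one profile per patient cannot separate from patient variance, so they can be too narrow

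*Protocol*

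**What the plan says.** Protocol 7.9.4 first assesses dose proportionality with a power model. If that points to a departure, and the data suffice, log dose-normalised AUC and Cmax go into a mixed model: "Dose will be fitted as a fixed effect and patient as a random effect". Each dose is compared with the lowest dose by a 90% confidence interval, and the intervals "will be constructed using the residual variance". For steady state, "The same analysis will be performed on" AUCss and Css,max from Cycle 2 Day 1.

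The sampling plan for escalation is in 6.5.1.1. For the single dose: "Time points on Cycle 0 Day 1 are pre-dose, 0.5, 1, 2, 3, 4, 6, 8, 10, 12, 24, 48, 72, 120 and 168 hours" after dosing. For steady state: "Time points on Cycle 2 Day 1 are pre-dose, 0.5, 1, 2, 3, 4, 6, 8, 10, 12 and 24 hours post-dose". The other scheduled escalation samples are pre-dose only.

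Protocol 7.9.6 compares low-fat-meal and fasted exposure on the same Cycle 2 Day 1 parameters with a plain linear model that has no patient term.

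**The concern.** A random patient effect separates between-patient from within-patient variation only if at least some patients contribute more than one value. Here the single-dose and steady-state data are analysed in separate runs, and each run has one value per patient at one dose. The model therefore contains two variance components that the data cannot tell apart. The interval rule then picks one of them, the residual.

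Dose groups are made up of different patients, so the error of a dose contrast is the full patient-to-patient variation. A rule that leaves out whatever share the software assigns to patient understates that error. At stake is the precision reported for the dose-normalised exposure ratios. The fallback runs when a departure is already suspected, so an over-narrow interval could overstate a departure at particular doses. Two analysts with different software defaults could also report different intervals from the same data.

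**Working it through.** **Is there replication within patient?**
- Escalation (6.5.1.1, Table 5): one full profile at Cycle 0 Day 1 and one at Cycle 2 Day 1, analysed separately.
- Expansion (6.5.1.2, Table 7): one full profile per occasion.
- Food-effect cohort (5.1.3, 6.5.1.1, Table 6): two single-dose profiles per patient, but at one defined dose and analysed in 7.9.5; only a pre-dose sample at Cycle 2 Day 1. If these replicates were pooled in, the residual would become within-patient variance, which is still the wrong yardstick for comparing doses between patients.
- Dose increase approved by the Safety Review Committee (5.1.1.6): no second full profile is scheduled.

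Each run therefore has one value per patient.

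**Identifiability.** Write y = dose mean + b + e, with variances σ_b² (patient) and σ_e² (residual). With one value per patient, every observation has variance σ_b² + σ_e² and all are independent, so the likelihood depends only on the sum. The REML log-likelihood was evaluated on simulated data with 5 doses. At patient shares of 0, 25, 50, 75, 90 and 100% it was the same throughout: −1.407648 with 6 per dose, 3.924952 with 3 per dose.

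**Effect on the interval.** With m patients per dose:
- correct contrast variance = (σ_b² + σ_e²) × 2/m
- residual-only variance = σ_e² × 2/m
- with patient share ρ = σ_b²/(σ_b² + σ_e²), width ratio = √(1 − ρ)
- actual coverage = 2·F_t(t_0.95 × √(1 − ρ)) − 1, with 5m − 5 degrees of freedom

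Inputs: 3 to 6 evaluable patients per cohort (5.1.1.1) and about 5 cohorts, about 30 patients (7.2.1; 5 × 6 = 30 agrees). Degrees of freedom are 25 for m = 6 and 10 for m = 3. The share ρ is an assumption: the documents give no value, and these data cannot estimate one. The plan states no precision figure for this analysis, so there is none to reproduce.

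| Assumed patient share ρ | Width ratio | Coverage, m = 6 | Coverage, m = 3 |
|---|---|---|---|
| 0% | 1.000 | 0.900 | 0.900 |
| 25% | 0.866 | 0.848 | 0.852 |
| 50% | 0.707 | 0.762 | 0.771 |
| 75% | 0.500 | 0.599 | 0.614 |
| 90% | 0.316 | 0.406 | 0.421 |

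**On the ratio scale.** The limits are the estimate multiplied and divided by exp(t_0.95 × s × √(2/m)), with s² = ln(1 + CV²). For an assumed between-patient CV of 50% and m = 6, the factor is 1.59 with total variance and 1.39 with residual only at a 50% split. For CVs of 30% to 70% the factors are 1.34 to 1.86 and 1.23 to 1.55.

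**What software may do.** One trial REML fit to simulated data (5 doses, 6 per dose) split the variance equally, 0.0701 and 0.0701, against an ordinary least-squares variance of 0.1403. It warned that the Hessian was not positive definite. Its printed contrast standard error was 0.184, against 0.216 from least squares.

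**The case against.** The strongest reply is that little is actually broken. In theory the point estimates, the total variance and the model-based standard error of a dose contrast do not depend on the split. If the patient variance is set to zero, or the interval uses the sum of the components, it is correct. That stands, so a reader who inferred that the dose comparison as a whole cannot be estimated would go too far. The fault lies in the instruction to use the residual variance, and in what software may print from a singular fit.

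Second, SAP section 1 says that Part A analyses are in a separate plan. That plan is not available and may specify something else. This also stands, but the protocol text would still have to agree with it.

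Third, patients may be moved to a higher dose and PK timing may be adjusted, so repeat profiles could arise and make a patient effect estimable. This is possible, but none is scheduled. The condition that data be sufficient does not help either: more patients add no replication within patient.

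Fourth, the coverage figures rest on assumed splits. That is true; they show a range, not what this trial's data would give.

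**Conclusion.** The interval rule is wrong as written, and its consequence is limited. A residual-only interval for a between-patient dose contrast is correct only at a patient share of zero and is otherwise too narrow; it cannot be too wide by this route. Illustrative coverage with 6 per dose is about 85%, 76% and 60% at assumed shares of 25%, 50% and 75%. This assumes normal log-scale data with equal variance across doses, t-based intervals on 25 degrees of freedom, and the residual component taken literally.

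A reader might infer that this undermines the statement in Protocol 2.3.5 of approximately dose-proportional exposure over 50 to 400 mg, or the choice of Part B doses. The documents do not support that. The fallback follows the power model and runs only on signs of a departure, 2.3.5 mentions no mixed model, and no acceptance bound or decision is tied to these intervals. The Part B primary endpoint is untouched. Nor does the point establish that the power model must change: its intercept is described as depending on patients, which is unclear, but nothing here shows an error in the slope.

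**What to change.** In Protocol 7.9.4, drop the patient term. Fit a one-way linear model of log dose-normalised AUC and Cmax on dose, with intervals from the pooled between-patient mean square, separately for Cycle 0 Day 1 and Cycle 2 Day 1. This is consistent with 7.9.6 and restores nominal 90% coverage under normality and equal variance. The smaller alternative is to keep the model and state that the intervals use patient plus residual variance. Either way, check that the Part A analysis plan matches.

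The cost is a sentence in the protocol and, if needed, one in the Part A plan. Point estimates do not change; intervals may be wider.

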7.9.5 The effect of high fat meal

For the assessment of the effect of high fat meal, the primary PK variables $AUC_{(0-\infty)}$ and/or $AUC_{(0-t)}$ and/or $AUC_{(0-t)}$, and C_{max} of plasma DZD9008 will be analyzed in food effect analysis set. These parameters will be natural log-transformed and analyzed using a linear mixed effects model with fixed effects for sequence, period and treatment, and random effect for patient nested within sequence. The difference in treatment means will be determined along with its associated 90% CI and back-transformed to give an estimate of the effect of food on the exposure of DZD9008. The results of this analysis will be presented in terms of geometric means for both treatments, the effect of food on the exposure of DZD9008 (ie, the ratio of the treatment geometric means) and its 90% CI.

Date: July 24,2023

In the event of relevant carry-over exposure across periods (predose concentration exceeds 5% of C_{max} for DZD9008 in period 2), the primary analysis will be performed excluding the Period 2 data for patients meeting the carry-over criteria. A secondary statistical analysis may be performed including all patients, irrespective of the degreee of carry-over. If appropiorate, an exploratory analysis on carry-over adjusted concentrations and PK parameters may also be performed.

7.9.6 The effect of low-fat meal

Additional cohorts from Part A investigate PK exposure of DZD9008 at 200 mg and 300 mg, respectively, with low-fat meal. For the assessment of the effect of low-fat meal, the primary PK parameters at steady state (AUC_{ss} and C_{ss,max} at cycle 2 day 1) will be analyzed. These parameters will be natural log-transformed and analyzed using a linear model, with the dose level (200 mg or 300 mg) and food condition (fed or fasted) included as independent variables. The between-food condition difference and 90% confidence intervals (CIs) will be provided.

An evaluable full PK profile between fasted and fed was defined as:

On C2D1 of Part A expansion, the patient took DZD9008 under the originally assigned prandial conditions.

No vomiting occurred within four hours following dose administration on the full PK sampling day.

Additionally, an entire PK profile could be considered non-evaluable as per scientific judgment of clinical pharmacology expert even if the above criteria were fulfilled.

7.9.7 Efficacy

Efficacy endpoints related to RECIST tumor assessment will be analyzed and reported based on the evaluation by IRC and investigators, respectively.

Unless otherwise specified, the efficacy analysis population will be the evaluable for response anlaysis set for Part A and full analysis set for Part B. To support companion diagnostics development, efficacy analysis in centrally confirmed EGFR Exon20ins by tumor tissue and centrally confirmed EGFR Exon20ins by plasma ctDNA analysis sets may be performed for Part B.

7.9.7.1 Tumor response

The analysis population will be the evaluable for response analysis set for Part A and FAS for Part B.

Summaries of the number of patients with best overall response in each part will be provided in the following categories: Complete Response (CR), Partial Response (PR), Stable Disease (SD), Progressive Disease (PD) and Non-Evaluable (NE). Objective response rate and disease control rate will be summarized.

For Part B, p value for the test against the null hypothesis of ORR \le 17\% will reported based on the Simon's two-stage method. ORR and two-sided 97.5\% CI will be calculated based on Jung's method (26) to adjust the bias caused by optional sampling in the Simon's two-stage design and provide the uniformly minimum variance unbiased estimator.

Date: July 24,2023

Data will be analyzed by subgroup (e.g. taken into consideration of the prior treatment) in Part B.

7.9.7.2 **Duration of response**

The analysis population for duration of response will be the subset of the evaluable for response population (Part A) or FAS (Part B) with a best overall response of confirmed CR/PR. Duration of response will be summarized and the number (%) of responding patients with a duration of response > 3, > 6, > 9 and > 12 months will be presented. Or if data are appropriate, response ongoing rates at 6, 9 and 12 months will be estimated based on Kaplan-Meier method. A Kaplan Meier plot and median duration of response (calculated from the Kaplan-Meier) will be presented.

7.9.7.3 Change in tumor size

The analysis population for change in tumor size will be the evaluable for response set for Part A and FAS for Part B.

The absolute values and percentage change in target lesion tumor size from baseline will be summarized using descriptive statistics and presented at each time point. The best change will also be summarized.

Tumor size will also be presented graphically using waterfall plots, presenting each patient's percentage change in tumor size as a separate bar, with the bars ordered from the largest increase to the largest decrease. Reference line at the -30% change in tumor size levels will be added to the plots, which corresponds to the definition of partial response.

7.9.7.4 Progression free survival

The analysis populations for PFS will be the safety analysis set for Part A and FAS for Part B.

PFS will be displayed using a Kaplan-Meier plot. The progression-free survival rates at 6, 9 and 12 months (calculated from the Kaplan-Meier estimator), median and quartiles (if estimable from the Kaplan-Meier estimator) will be summarized.

7.9.7.5 Overall survival

Overall survival will be analyzed and reported in FAS for Part B. The survival status (dead, alive, lost to follow-up, etc) at the end of the study will be summarized. In addition, the number and percentage of patients prematurely censored before data cut-off will be summarized.

Overall survival will be displayed using a Kaplan-Meier plot. The overall survival rates at 6, 9 and 12 months (calculated from the Kaplan-Meier estimator), median and quartiles (if estimable from the Kaplan-Meier estimator) will be summarized.

7.9.8 Patient Report Outcome (PRO)

Descriptive analysis will be perfored by treatment group and visit for each item and the VAS score in EQ-5D-5L.

7.9.9 PoM biomarker

The pharmacodynamic effect of DZD9008 on pEGFR in tumor tissue from paired biopsies will be evaluated. The technological platform for the pharmacodynamics analysis will be

Date: July 24,2023

immunohistochemistry, but may not be limited to this. The biomarker study will include, but not limit to pEGFR pEGFR expression in tumor tissue with DZD9008 treatment will be summarized and displayed graphically in subset of patient population who have paired tumor tissue biopsies. The baseline and post-treatment pEGFR levels will be compared for individual patient and will be also summarized by dose cohort.

PoM biomarker study result will not constitute the Clinical Study Report.

